10.1.4. Data Protection

Participants will be assigned a unique identifier by the sponsor. Any participant records or datasets that are transferred to the sponsor will contain the identifier only; participant names or any information which would make the participant identifiable will not be transferred. The participant's consenting parent must be informed that the infant's medical records may be examined by Clinical Quality Assurance auditors or other authorized personnel appointed by the sponsor, by appropriate EC/IRB members, and by inspectors from regulatory authorities.

The participant's mother, and the other consenting parent or legal guardian if not the mother, must be informed that the mother's and infant's personal study-related data will be used by the sponsor in accordance with local data protection law. The level of disclosure must also be explained.

10.1.5. Dissemination of Clinical Study Data

10.1.6. Data Quality Assurance

All participant data relating to the study will be recorded by an eCRF using an electronic data capture (EDC) system transmitted to the sponsor or designee electronically (e.g., laboratory data). The investigator is responsible for verifying that data entries are accurate and correct by electronically signing the eCRF.

The investigator must maintain accurate documentation (source data) that supports the information entered in the eCRF.

The study will be monitored regularly by the sponsor or its designee throughout the study period.

The investigator must permit study-related monitoring, audits, IRB/EC review, and regulatory agency inspections and provide direct access to source data documents.

Monitoring details describing strategy (e.g., risk-based initiatives in operations and quality such as Risk Management and Mitigation Strategies and Analytical Risk-Based Monitoring), methods, responsibilities and requirements, including handling of noncompliance issues and monitoring techniques (central, remote, or on-site monitoring) are provided in the Monitoring Plan.

The sponsor or designee is responsible for the data management of this study including quality checking of the data.

The sponsor assumes accountability for actions delegated to other individuals (e.g., CRO).

Study monitors will perform ongoing source data verification to confirm that data entered into the eCRF by authorized site personnel are accurate, complete, and verifiable from source documents; that the safety and rights of participants are being protected; and that the study is being conducted in accordance with the currently approved protocol and any other study agreements, ICH GCP, and all applicable regulatory requirements.

10.1.7. Record Retention

Records and documents pertaining to the conduct of this study must be retained by the investigator for a minimum of 10 years after study completion unless local regulations or institutional policies require a longer retention period.

No records may be destroyed during the retention period without the written approval of the sponsor. No records may be transferred to another location or party without written notification to the sponsor.

10.1.8. Source Documents

Source documentation consists of existing medical records and/or study records developed and maintained by the investigator. Source documents provide evidence for the existence of the participant and substantiate the integrity of the data collected and are to be filed at the investigator's site. Data recorded on source documents will be transcribed onto eCRFs using an EDC system.

Data entered in the eCRF that are transcribed from source documents must be consistent with the source documents or the discrepancies must be explained. The investigator may need to request previous medical records or transfer records, depending on the study.

For the purpose of monitoring and auditing the study, source documentation will consist of existing medical records and/or study records developed and maintained by the investigator.

10.1.9. Study and Site Closure

The sponsor designee reserves the right to close the study site or terminate the study at any time for any reason at the sole discretion of the sponsor. Study sites will be closed upon study completion. A study site is considered closed when all required documents and study supplies have been collected and a study site closure visit has been performed.

The investigator may initiate study site closure at any time, provided there is reasonable cause and sufficient notice is given in advance of the intended termination. Reasons for the early closure of a study site by the sponsor or investigator may include but are not limited to:

- failure of the investigator to comply with the protocol, the requirements of the EC/IRB or local health authorities, the sponsor's procedures, or GCP guidelines
- inadequate recruitment of participants by the investigator
- discontinuation of further study intervention development.

At the discretion of the sponsor, all materials and supplies provided to the investigator will be returned or disposed of in compliance with local regulatory requirements upon authorization from the sponsor, upon study completion. The investigator or designated clinical site staff will notify the EC/IRB when the study has been completed.

10.1.10. Publication Policy

The results of this study may be published or presented at scientific meetings. If this is foreseen, the investigator agrees to submit all manuscripts or abstracts to the sponsor before submission. This allows the sponsor to protect proprietary information and to provide comments.

The sponsor will comply with the requirements for publication of study results. In accordance with standard editorial and ethical practice, the sponsor will generally support publication of multicenter studies only in their entirety and not as individual site data. In this case, a coordinating investigator will be designated by mutual agreement.

Authorship will be determined by mutual agreement and in line with International Committee of Medical Journal Editors authorship requirements.

10.1.11. Financing and Insurance

Financing and insurance information is provided as a separate agreement.

10.2. Adverse Events and Serious Adverse Events: Definitions and Procedures for Recording, Evaluating, Follow-up, and Reporting

10.2.1. Definition of AE

AE Definition

An AE is any untoward medical occurrence in a patient or clinical study participant, temporally associated with the use of study intervention, whether or not considered related to the study intervention.

NOTE: An AE can therefore be any unfavorable and unintended sign (including an abnormal laboratory finding), symptom, or disease (new or exacerbated) temporally associated with the use of study intervention.

Events Meeting the AE Definition

Any abnormal laboratory test results (hematology, clinical chemistry, or urinalysis) or other safety assessments (e.g., ECG, radiological scans, vital signs measurements), including those that worsen from baseline, considered clinically significant in the medical and scientific judgment of the investigator (i.e., not related to progression of underlying disease).

Exacerbation of a chronic or intermittent pre-existing condition including either an increase in frequency and/or intensity of the condition.

New conditions detected or diagnosed after study intervention administration even though it may have been present before the start of the study.

Signs, symptoms, or the clinical sequelae of a suspected drug-drug interaction.

Signs, symptoms, or the clinical sequelae of a suspected overdose of either study intervention or a concomitant medication. Overdose per se will not be reported as an AE/SAE unless it is

an intentional overdose taken with possible suicidal/self-harming intent. Such overdoses should be reported regardless of sequelae.

Events **NOT** Meeting the AE Definition

Any clinically significant abnormal laboratory findings or other abnormal safety assessments which are associated with the underlying disease, unless judged by the investigator to be more severe than expected for the participant's condition.

The disease/disorder being studied or expected progression, signs, or symptoms of the disease/disorder being studied, unless more severe than expected for the participant's condition.

Medical or surgical procedure (e.g., endoscopy, appendectomy): the condition that leads to the procedure is the AE.

Situations in which an untoward medical occurrence did not occur (social and/or convenience admission to a hospital).

Anticipated day-to-day fluctuations of pre-existing disease(s) or condition(s) present or detected at the start of the study that do not worsen.

10.2.2. Definition of SAE

If an event is not an AE per definition above, then it cannot be an SAE even if serious conditions are met.

An SAE is defined as any untoward medical occurrence that, at any dose:

i. Results in death

j. Is life-threatening

The term 'life-threatening' in the definition of 'serious' refers to an event in which the participant was at risk of death at the time of the event. It does not refer to an event, which hypothetically might have caused death, if it were more severe.

k. Requires inpatient hospitalization or prolongation of existing hospitalization

In general, hospitalization signifies that the participant has been detained (usually involving at least an overnight stay) at the hospital or emergency ward for observation and/or treatment that would not have been appropriate in the physician's office or outpatient setting. Complications that occur during hospitalization are not necessarily SAEs. If a complication prolongs hospitalization or fulfills any other serious criteria, the event is serious. When in doubt as to whether "hospitalization" occurred or was necessary, it should be considered as an SAE.

Hospitalization for elective treatment of a pre-existing condition that did not worsen from baseline is not considered an adverse event.

I. Results in persistent disability/incapacity

- The term disability means a substantial disruption of a person's ability to conduct normal life functions.
- This definition is not intended to include experiences of relatively minor medical significance such as uncomplicated headache, nausea, vomiting, diarrhea, influenza, and accidental trauma (e.g., sprained ankle) which may interfere with or prevent everyday life functions but do not constitute a substantial disruption.

m. Is a congenital anomaly/birth defect

n. Other situations:

• Medical or scientific judgment should be exercised in deciding whether SAE reporting is appropriate in other situations such as important medical events that may not be immediately life-threatening or result in death or hospitalization but may jeopardize the participant or may require medical or surgical intervention to prevent one of the other outcomes listed in the above definition. These events should usually be considered serious.

Examples of such events include invasive or malignant cancers, intensive treatment in an emergency room or at home for allergic bronchospasm, blood dyscrasias or convulsions that do not result in hospitalization, or development of drug dependency or drug abuse.

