5.1. Inclusion Criteria

Participants are eligible to be included in the study only if all of the following criteria apply:

Age

1. Participant must be between 30 days and 120 days of age (inclusive), at the time of enrollment (study Day 1)

Type of Participant and Disease Characteristics

- 2. Hospitalized for acute non-surgical illness
- 3. Completed acute stabilization phase of treatment, including fluid rehydration and antibiotic course, prior to enrollment (study Day 1)

Weight

4. WAZ at enrollment (study Day 1) is less than negative 2 (<-2)

Sex

5. Any

Informed consent

6. Participant's parent(s)/legal guardian is capable of giving informed consent which includes agreement to comply with the requirements and restrictions listed in the informed consent form (ICF) and in this protocol

Additional requirements

- 7. Participant's parent(s)/legal guardian agrees to stay in contact with the study site for the duration of the study, provide updated contact information as necessary, and have no current plans to relocate from the study area for the duration of the study
- 8. Participant's parent(s)/legal guardian has easy access to reliable refrigeration (for storage of investigational product)
- 9. Participant receives some feedings from breastmilk and mother intends to continue breast-feeding.

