Log-binomial regression will be used to estimate the risk ratio of re-hospitalization rates at Day 56 between Bi-26 and Placebo, adjusting for covariates baseline WAZ, age (in days), country and discharge destination. The adjusted risk ratio (exponentiated coefficient) with 95% CI will also be presented in the same summary table. If the overall re-hospitalization rate is less than 15% of all participants or the log-binomial model does not converge, then logistic regression will be used in the place of log-binomial regression. Odds ratios will be reported instead of risk ratios, which will be a reasonable estimate of the risk ratios.

PROC GLIMMIX will be used for this analysis.

Confidential Page 36 of 50

Re-hospitalizations for acute non-surgical illness will be listed in a separate listing for all participants, including date/time of admission, associated SAE, preferred term of SAE and date/time of discharge if discharged.

The Safety and PP populations will be used for this analysis.

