11.6.1 Adverse Events

Safety assessments include SAEs and AEs from the time the ICF is signed through Day 90 (or at the date of last visit/study discontinuation).

An AE is considered treatment emergent if it started on or after the date of first dose of study intervention administration.

Confidential Page 37 of 50

An AE overview table containing the number and percentage (expressed in percent) of participants with AEs from Day 1 through Day 90 will be summarized by treatment group for the following:

- Any AE
- Any TEAE
- TEAEs related to study intervention
- TEAEs by maximum severity (Mild, Moderate and Severe)
- TEAEs leading to study intervention discontinuation
- TEAEs leading to study withdrawal
- Serious TEAEs
- Serious TEAEs with Outcome of Death

Additionally, the number and percentage of participants with AEs will be provided by SOC and PT and by treatment group for the following:

- Any TEAE
- TEAEs by maximum severity
- TEAEs related to study intervention
- Serious TEAEs
- Serious TEAEs related to study intervention

By-period summaries will be presented for TEAE and serious TEAEs by treatment group, where period is defined as in Section 10.1.

The overall AE summary table, AE table by SOC and PT and SAE table by SOC and PT will be presented by subgroups as specified in Section 8.2.

All AEs and SAEs will be classified according to the latest version of MedDRA.

SOC and PT will be sorted alphabetically by SOC and by decreasing frequency of preferred term in the all Bi-26 group (then alphabetically for ties). If a participant has more than one AE at a given level (eg, SOC and preferred term), the participant will only be counted once within that level. All summary tables will include the number of AEs. Missing severities and relationship will not be regarded as 'worst case'.

The following listings will be presented:

- All AEs through to Day 90
- SAEs through to Day 90

The AE listing by participant will display all reported AEs up to Day 90 and will include the verbatim term in addition to the SOC and preferred term. This listing will also include all relevant data associated with the event: eg, date of onset, date resolved, date of first dose, date of last dose, severity, whether AE is serious, outcome, relationship to study intervention, action taken with study intervention, and required therapy. When a date is presented, the study day

Confidential Page 38 of 50

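### Deaths and unplanned readmissions judged to be expected progression of undernutrition can fall outside SAE reporting, and such deaths outside the SAP's only specified by-arm death count

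*Protocol*

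**What the plan says.** - Protocol 10.2.1, among events that are not AEs: "The disease/disorder being studied or expected progression, signs, or symptoms of the disease/disorder being studied, unless more severe than expected for the participant's condition". Neither document defines the disease or disorder being studied.
- Protocol 10.2.2, before the seriousness criteria: "If an event is not an AE per definition above, then it cannot be an SAE even if serious conditions are met". Death and inpatient hospitalisation appear in the criteria that follow, with no exception to this sentence for either.
- Protocol 10.2.1, among events that are AEs: "Exacerbation of a chronic or intermittent pre-existing condition including either an increase in frequency and/or intensity of the condition" and "New conditions detected or diagnosed after study intervention administration even though it may have been present before the start of the study".
- Protocol 8.4.1 applies the 24-hour reporting duty to SAEs.
- SAP 11.6.1 tabulates by treatment group a line for "Serious TEAEs with Outcome of Death". SAP 11.6.2 adds a participant listing of deaths, with the primary cause and a field on whether the studied condition played a part. It specifies no by-arm table.
- Protocol Table 1 defines the re-hospitalisation endpoint as a number of readmissions up to Day 56, not as a count of SAEs. The listing in SAP 11.5.7 includes "associated SAE, preferred term of SAE and date/time of discharge if discharged".

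**The concern.** The two protocol rules form a chain. If an event is expected progression of the disease under study, it is not an AE; if it is not an AE, it cannot be an SAE, even when the infant dies or is admitted. The only brake is whether the event was more severe than expected, and the protocol gives no yardstick for that in a population it describes as being at high risk of death.

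At stake are 24-hour reporting of such events, their place in the SAE tables, and the completeness of the by-arm death count. Sites may also apply the exclusion differently. If the product did harm through poor growth or decline, some of that harm would appear as the very events an investigator might call progression.

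**Working it through.** The point rests on wording, so the main check is to read the passages together. The arithmetic only shows scale.

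**1. Which disease is excluded?** The trial enrols infants with WAZ below -2. Protocol 5.1 also requires "Hospitalized for acute non-surgical illness", under a heading that covers disease characteristics. Undernutrition is the natural reading of the disease under study. The index illness is a possible but weaker reading, because infants must have completed acute stabilisation before Day 1 and a new illness after dosing is an AE.

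**2. Does other text override the chain?**
- The lines on exacerbations and new conditions bring many events back. For worsening undernutrition, however, the exacerbation line and the progression exclusion pull in opposite directions, and 10.2.1 does not say which prevails.
- The instruction in 10.2.2 to treat doubtful hospitalisations as SAEs concerns whether an admission took place or was needed. It does not address whether the event is an AE.
- The statement in 8.4.1 that all AEs and SAEs are collected relies on the same definitions.

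No text makes deaths or admissions reportable regardless of cause.

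**3. What depends on SAE status?**
- *Deaths by arm:* the SAP 11.6.1 line counts only deaths that are the outcome of a serious treatment-emergent AE. The field in the 11.6.2 listing on the contribution of the studied condition shows that the SAP expects deaths of the kind 10.2.1 may exclude.
- *Readmissions:* Protocol 8.2 refers to the Schedule of Activities for timing, but Table 2 has no readmission row. At home visits the row for AEs and SAEs is the only one that records clinical events; interim history is taken at clinic visits. The SAP listing expects a linked SAE. The capture route is therefore unstated.

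**4. Scale.** Inputs from Protocol 9.4: N = 396 (198 per arm) and assumed mortality 3%.
- Expected deaths = 396 × 0.03 = 11.9, about 12.
- Per arm = 198 × 0.03 = 5.9, about 6.

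Let f be the share of deaths classed as expected progression. The documents give no value, so the following are assumptions. Deaths reported as SAEs = 11.9 × (1 − f):

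| f | Deaths reported as SAEs |
|---|---|
| 0% | 11.9 |
| 25% | 8.9 |
| 50% | 5.9 |
| 75% | 3.0 |
| 100% | 0 |

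If f is the same in both arms, as blinding makes plausible, the expected difference between arms shrinks by the factor (1 − f). As an assumed example, a true split of 8 against 4 would be expected to show as 4 against 2 at f = 50%.

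**The case against.** The strongest reply is that the gap is narrow and the trial has other ways to see these events. Much of that stands.

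- **Infections.** A reader might infer that infections in general can be left out. The documents do not support that: new conditions and exacerbations are AEs under 10.2.1.
- **Deaths lost altogether.** A reader might infer this too, but SAP 11.6.2 lists deaths with cause. The disposition table in SAP 11.1 also gives reasons for withdrawal by treatment, which may include death, although the categories are not stated. What remains is that no complete by-arm death count is specified.
- **Re-hospitalisation.** It is tempting to say that this endpoint depends wholly on SAE capture. It is defined in its own right, and the linked SAE is one item in a listing. An unstated route is not the same as an SAE-only route.
- **The monitoring committee.** A reader might infer that the IDMC would not see these deaths. Protocol 8.4.5 and SAP 7.1.2 speak of unblinded safety data in general, and the charter that governs its outputs is not among the documents. It may cover all deaths, although it would not change the site definitions or the SAP tables.
- **Larger numbers.** Applying the 8.7% three-month mortality in Protocol section 2 to everyone gives 396 × 0.087 = 34.5, about 34 deaths. That rate comes from severely underweight children under 5 with pneumonia. Only about one third of this trial is targeted at WAZ of -3 or below, and 132 × 0.087 is about 11. The closer population, underweight infants under 6 months, had 5.3% after discharge over a year. Section 2 gives mortality, not readmission rates, so it does not show that readmission is common.

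None of this removes the core point: the bar in 10.2.2 is absolute, and the severity clause leaves the decision to individual judgement.

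**Conclusion.** The concern holds in a limited form. As written, 10.2.1 and 10.2.2 allow a death or unplanned readmission judged to be expected progression of undernutrition to escape SAE reporting, and allow such a death to be missing from the SAP's only specified by-arm death count. The case is weaker for the index illness. Events can, not will, be lost in this way.

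About 12 deaths are expected (about 6 per arm) if the planned 3% mortality applies to all 396 infants. The number affected cannot be estimated, because the share that investigators would class as progression is unknown. With so few deaths expected, even a handful of reclassifications would matter to a safety comparison, and correcting the rule is cheap. It should be changed rather than left to site judgement.

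**What to change.** 1. **Protocol 10.2.1 and 10.2.2.** State that every death, and every unplanned hospital admission after the Day 1 discharge, is recorded as an SAE regardless of cause, including events judged to be progression of undernutrition or of the index illness. Counting admissions from the Day 1 discharge matters because infants are already in hospital when consent is given. Keep the existing exclusions for social or convenience admissions, for elective admissions and for non-serious fluctuation. Define the disease under study.
2. **SAP 11.6.2.** Add a by-arm count of all deaths taken from the death record, beside the SAE-based line in 11.6.1.

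The cost is a short protocol amendment with notice to sites, some extra SAE forms that carry the 24-hour reporting duty, and one extra table. The change concerns recording and tabulation only, not care.
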